6.6.2 Secondary Efficacy Endpoints

Secondary endpoints that are binary will be analyzed using similar methods used for analyzing the primary endpoint.

Continuous secondary endpoints will be analyzed using a Mixed Model for Repeated Measures (MMRM) approach incorporating all observed data up to 12 weeks of treatment. The MMRM will include the absolute change from baseline as the dependent variable. The fixed effects in the model will include treatment, visit (week), treatment-by-visit (weeks) interaction, along with baseline score as continuous covariates. An unstructured variance-covariance structure will be applied to model the within-patient errors, and the restricted maximum likelihood method will be used for estimating the variance components. The denominator degrees of freedom will be estimated using *the Kenward-Roger approximation*.

The least squares mean of change from baseline for each treatment group together with a 95% CI will be calculated from the MMRM model for each visit. At Week 12, the placebo-corrected difference will be estimated from the same MMRM model and will be used to test the null hypothesis of zero difference.

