Continuous secondary endpoints will be analyzed using a Mixed Model for Repeated Measures (MMRM) approach incorporating all observed data up to 12 weeks of treatment. The MMRM will include the absolute change from baseline as the dependent variable. The fixed effects in the model will include treatment, visit (week), treatment-by-visit (weeks) interaction, along with baseline score as continuous covariates. An unstructured variance-covariance structure will be applied to the model.

Additional exploratory analyses will be conducted if deemed appropriate.

PHARMACODYNAMIC ANALYSES

All pharmacodynamic parameters will be presented by listings and descriptive summary statistics separately by treatment group.

PHARMACOKINETIC ANALYSES

The population methods used for modelling of plasma concentration data will be described separately.

SAFETY ANALYSES

Safety data presentations will include all subjects who received at least one dose of the study medication. For these analyses, patients will be grouped according to the treatment actually received.

SAMPLE SIZE JUSTIFICATION

A total of 70 patients will be randomized in a 1:1 ratio to RO5459072 or placebo treatment groups.

A total of 70 patients (35 per treatment group) will provide a power in the range of at least 58 % to 80 % to detect a difference in ESSDAI response rates between treatment groups in the range of 25 % to 33 % (two-sided Chi-square test assuming alpha of 0.05 and placebo response rate \leq 25%). This sample size was determined by practical considerations. Seventy patients also provides approximately 70% power to detect a difference of 3-points between treatment groups in change from baseline in ESSDAI score (t test assuming two-sided alpha of 0.05 and standard deviation of 5.0).

Approximately 30 patients will be enrolled into the optional sub-study. It is anticipated that enrollment of 30 patients should ensure at least 20 patients (10 per treatment group) complete the study and have biopsy samples taken at both baseline and Week 12, assuming a maximum drop-out rate of 15%.

CONCOMITANT MEDICATIONS

In addition to the study drug treatment, patients may continue to concomitantly use existing treatments for Sjögren's syndrome.

Prohibited therapies are:

- Corticosteroid therapy exceeding 7.5 mg prednisone equivalent per day.
- Anti-CD20 therapy (e.g., rituximab) or other B cell-depleting therapy within 6 months of screening.

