Appendix 1 Schedule of Assessments

Visit ⁸	Screening	Baseline ¹	Treatment Period				Follow-Up Visit	Early Termination Visit
			Week 2	Week 6	Week 9	Week 12		
Days	-28 to -8	-7 to -1	14 (± 7)	42 (± 7)	63 (± 7)	84 (± 7)	98 (± 7)	(NA)
Informed Consent	x							
Randomization		x						
Study drug dispensing		x	x	x				
Study drug return				x		x		x
Entry criteria	x	x						
Demography	x							
Medical History	x							
Physical Examination ²	x						x	x
Pregnancy testing ³	x	x	x	x	x	x	x	x
Tuberculosis testing	x							
HIV, HBV and HCV testing	x							
Clinical Genotyping		x						
ESSDAI score	x	x		x		x	x	x
ESSPRI score	x	x	x	x	x	x	x	x
SF-36		x		x		x		
Salivary samples ⁴		x	x	x		x		
Saliva flow assessment		x	x	x		x		
Tear samples ⁴		x	x	x		x		
Tear flow assessment		x	x	x		x		
mRNA sample		x	x	x		x		
Autoantibodies	x	x		x		x	x ⁵	x ⁵
Soluble biomarkers		x	x	x		x		
Immunophenotyping		x	x	x		x		
Cathepsin S activity/ mass		x	x	x		x		
ESR test		x	x	x		x		
PK sample			x	x		x		
Safety laboratory assessments ⁶	x	x	x	x	x	x	x	x
ECG - 12 Lead	x	x	x	x	x	x	x	x
Vital Signs	x	x	x	x	x	x	x	x
MSG biopsy (optional sub-study only)		x				x ⁷		
Adverse Event or Intercurrent Illness	x							
Previous and Concomitant Treatments								

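### The MMRM gives baseline one slope for all visits; if correlation with baseline fades, the Week 12 contrast loses some precision, mainly for ESSPRI, and a baseline-by-visit term would recover it cheaply

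*Combined protocol and SAP*

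**What the plan says.** Section 6.6.2 sets out the analysis of the continuous secondary endpoints almost completely.

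- Outcome: "The MMRM will include the absolute change from baseline as the dependent variable".
- Fixed effects: "The fixed effects in the model will include treatment, visit (week), treatment-by-visit (weeks) interaction, along with baseline score as continuous covariates". The efficacy paragraph of the synopsis repeats the list, ending "along with baseline score as continuous covariates".
- Covariance: "An unstructured variance-covariance structure will be applied to model the within-patient errors", with REML and Kenward-Roger degrees of freedom.
- Data used: "incorporating all observed data up to 12 weeks of treatment".
- Test: "At Week 12, the placebo-corrected difference will be estimated from the same MMRM model".

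Neither place lists a baseline-by-visit interaction. In the schedule of assessments (Appendix 1), ESSPRI is collected on treatment at Weeks 2, 6, 9 and 12, and ESSDAI and SF-36 at Weeks 6 and 12. The opening of Section 6 defers analysis details to a statistical analysis plan; no separate SAP text on this model is in the documents supplied.

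**The concern.** The model lets the treatment effect and the residual covariance differ freely between visits but holds the effect of baseline constant. For a change score that constraint is often wrong. With equal SDs, the slope of change on baseline at a visit is the correlation with baseline minus 1, so it steepens as the correlation fades. A single slope is then a compromise dominated by the early visits, where patients still resemble their baseline, while the only visit tested is the last.

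At stake is the precision of the Week 12 contrasts, chiefly ESSPRI and its three components. The primary objective covers symptoms as well as disease activity, and Section 3.2.5 says ESSPRI and ESSDAI do not correlate, so ESSDAI cannot stand in for ESSPRI. The trial has 70 patients, its size was set on practical grounds, no power is given for ESSPRI, and Section 4.3.1 mentions no stratification by baseline score. Covariate adjustment is therefore the main protection against chance baseline imbalance.

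**Working it through.** **1. The plan's own figure.** Section 6.1: 35 per arm, difference 3, SD 5.0, two-sided alpha 0.05. Noncentrality = 3 / (5.0 × √(2/35)) = 3 / 1.195 = 2.51 on 68 df, giving power 69.7% against the stated 70% or so. This is an unadjusted t-test, so the covariate question does not touch it. The documents give no figure for the MMRM or for ESSPRI.

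**2. Inputs.** From the documents: 35 per arm and the visit schedules above. Assumed, because the documents give no correlations, baseline SD or ESSPRI SD: baseline-to-Week-12 correlation ρ from 0.3 to 0.7; ratio k of post-baseline to baseline SD of 1.0 or 1.4; and three correlation patterns, namely equal correlation at all gaps (compound symmetry), AR(1) decay, and AR(1) decay with measurement error (reliability 0.85 unless stated).

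**3. Formulas** (complete data, unstructured covariance, large sample, baseline SD = 1).

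- Slope of change on baseline at visit t: β_t = kρ_t − 1.
- Common slope b: the baseline coefficient when Week 12 change is regressed on treatment, baseline and the successive between-visit differences.
- Week 12 residual variance with slope b: V(b) = k² + (1 + b)² − 2(1 + b)kρ.
- With a baseline-by-visit term, Week 12 reduces to ANCOVA: V = k²(1 − ρ²).
- SE ratio = √[V(b) / V].

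**4. Worked case: ESSPRI, AR(1), ρ = 0.5, k = 1.** Visit slopes are −0.11, −0.29, −0.41 and −0.50; the common slope is −0.16 (−0.159 unrounded). V(b) = 1 + 0.841² − 2(0.841)(0.5) = 0.866, residual SD 0.931. The by-visit model gives 0.75, residual SD 0.866. Variance ratio 1.155, SE ratio 1.075. Matching 70 patients would take 70 × 1.155 = about 81.

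A one-SE baseline imbalance, √(2/35) = 0.24 SD, leaves 0.24 × (0.50 − 0.16) = about 0.08 SD unadjusted at Week 12.

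With k = 1.4 the common slope is +0.18 against −0.30 at Week 12. Its residual SD, 1.303, exceeds that of the unadjusted change, √(1.96 + 1 − 1.4) = 1.25.

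**5. Range of the excess Week 12 SE, common slope over by-visit, ρ = 0.3 to 0.7.**

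| Pattern | ESSPRI | ESSDAI, SF-36 |
|---|---|---|
| Equal correlation | 0% | 0% |
| Decay with error, reliability 0.85 | 0.6–4.0% | 0.2–0.8% |
| AR(1), no error | 4.9–8.5% | 1.3–1.5% |

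Raising the reliability to 0.9 takes the top of the ESSPRI decay-with-error range to about 5%. Steeper patterns go further. In separate simulations, baseline correlations of 0.8, 0.6, 0.5 and 0.4 at the four ESSPRI visits gave a variance ratio of 1.21 (SE √1.21 = 1.10), and 0.8 and 0.6 at the two ESSDAI visits gave 1.04 (SE about 1.02).

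**6. Simulation check.** 1,000 REML fits per scenario, 35 per arm, ρ = 0.5, k = 1. The 15% random dropout is borrowed from the biopsy sub-study in Section 6.1. Entries are SE ratios, common over by-visit, at 0% / 15% dropout.

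| Pattern | ESSPRI | ESSDAI |
|---|---|---|
| Equal correlation | 0.996 / 0.995 | 0.998 / 0.996 |
| Decay with error | 1.021 / 1.022 | 1.004 / 1.005 |
| AR(1) | 1.067 / 1.069 | 1.012 / 1.016 |

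Both models were unbiased for the Week 12 effect to within simulation error. The first row is the price of the extra term when it is not needed: about 0.2–0.5% of the SE. The reference distribution was t on Week 12 completers minus 3 df, not Kenward-Roger, and dropout depending on baseline was not simulated.

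**7. Power.** An ESSPRI effect with 80% power under the by-visit model has, under the common slope, 80% (equal slopes), 78.0% (decay with error, ρ = 0.5), 74.1% (AR(1), ρ = 0.5) or 73.3% (SE +8.5%). For a 3-point ESSDAI difference with SD of change 5.0 and AR(1) at ρ = 0.5, the residual SDs are 5 × 0.879 = 4.40 and 5 × 0.866 = 4.33, giving 80.4% against 81.5%.

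**The case against.** The strongest reply is that nothing in the documents shows that this trial would lose precision. Without correlations the loss is conditional, and with equal slopes it is nil. ESSPRI is the mean of three single 0–10 self-ratings, so some measurement error is to be expected, and error flattens the early slopes. The larger figures need an error-free process with a baseline-to-Week-2 correlation of 0.86–0.92 (Week 12 correlation 0.4–0.6); at reliability 0.8–0.9 and Week 12 correlation 0.5 the variance excess falls from 15.5% to about 3–7%. ESSDAI change, the only continuous endpoint with a stated power, is barely affected. These are secondary endpoints in a Phase 2a study, and a SAP could still add the term.

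Most of this stands, and it limits both size and severity. The deferral to a SAP carries less weight, because Section 6.6.2 already fixes the fixed effects, covariance, estimation method and degrees of freedom, and no supplied text adds the term. Equally, one cannot say that the final analysis will omit it.

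A reader might infer several stronger things that the documents do not support:

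- That Week 12 definitely is under-adjusted. This holds only if the correlation with baseline decays.
- That the result is biased. Both models estimated the Week 12 effect without bias; incomplete removal of chance imbalance is the same precision loss seen in a single trial.
- That a variance excess of around 10% or more is typical for ESSPRI. That depends on the assumed pattern and belongs to strong decay with little error.
- That the extra term is free. Its cost is negligible but not zero.

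**Conclusion.** The concern holds in conditional form. As written, the MMRM imposes one baseline slope on all visits, and if correlation with baseline fades, the one tested contrast is adjusted with a slope that is too shallow. Under the assumed patterns, the Week 12 SE for ESSPRI is larger by between 0% and about 8.5%, with up to about 4–5% when measurement error is allowed for and more only under steeper decay. For ESSDAI and SF-36 the excess is at most about 1.5–2%.

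These sizes rest on assumed correlations and SD ratios, and mainly on large-sample algebra supported by simulation with complete data or random dropout. Validity, the primary chi-square test and the stated power figures are not in question. This is a minor point: a cheap efficiency improvement, worth making because the possible gain for ESSPRI far exceeds the possible loss.

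**What to change.** Add a baseline-by-visit interaction to the MMRM fixed effects in Section 6.6.2 and the synopsis, or specify it in the SAP before unblinding. Keep the unstructured covariance, REML and Kenward-Roger degrees of freedom. It should be prespecified, since adding the term after unblinding would look data-driven.

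The cost is 3 extra parameters for ESSPRI (and for each of its components, which share its visits) and 1 each for ESSDAI and SF-36. If the slopes are in fact equal, the SE rises by about 0.2–0.5%. No new data, visits or patients are needed.

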6.7 PHARMACODYNAMIC ANALYSES

All pharmacodynamic parameters will be presented by listings and descriptive summary statistics separately by treatment group.

Pharmacodynamic variables at each assessment time-point along with corresponding changes from baseline will be listed by individual and summarized using descriptive summary statistics. Descriptive summary statistics will include the calculation of arithmetic means, standard deviation, coefficient variation, median, and range, as appropriate. Graphical plots of individual and mean absolute and change from baseline versus time profiles will also be produced for each treatment.

6.8 PHARMACOKINETIC ANALYSES

The population methods used for modelling of plasma concentration data will be described separately in the modelling report.

6.9 EXPLORATORY ANALYSES

Exploratory analyses will be conducted as deemed appropriate.

6.10 INTERIM ANALYSES

No interim analyses are planned for this study.

7. DATA COLLECTION AND MANAGEMENT

7.1 DATA QUALITY ASSURANCE

The Sponsor will be responsible for data management of this study, including quality checking of the data. Sites will be responsible for data entry into the Electronic Data Capture (EDC) system.

A comprehensive validation check program will verify the data. Discrepancies will be generated automatically in the system at the point of entry or added manually for resolution by the Investigator.

The Sponsor will produce a Data Handling Manual that describes the quality checking to be performed on the data. Laboratory electronic data will be sent directly to the Sponsor, using the Sponsor's standard procedures to handle and process the electronic transfer of these data.

System backups for data stored by the Sponsor and records retention for the study data will be consistent with the Sponsor's standard procedures.

The Sponsor will be responsible for data management of this study, including quality checking of the data. Sites will be responsible for data entry into the EDC system. In the event of discrepant data, the CRO will request data clarification from the sites, which the sites will resolve electronically in the EDC system.

7.2 ELECTRONIC CASE REPORT FORMS

Data for this study will be captured via an on line EDC system. The data collected in the source documents is entered onto the study eCRF. An audit trail will maintain a record of initial entries and changes made; reasons for change; time and date of entry; and user name of person authorizing entry or change. For each patient enrolled, an eCRF must be completed and electronically signed by the Principal Investigator or authorized delegate from the study staff. If a patient withdraws from the study, the reason must be noted on the eCRF. If a patient is withdrawn from the study because of a treatment-limiting adverse event, thorough efforts should be made to clearly document the outcome.

The Investigator should ensure the accuracy, completeness and timeliness of the data reported to the Sponsor/CRO in the eCRFs and in all required reports.

eCRFs will be submitted electronically to the Sponsor/CRO and should be handled in accordance with instructions from the Sponsor/CRO.

At the end of the study, the Investigator will receive patient data for his or her site in a readable format on a compact disc that must be kept with the study records.

Acknowledgement of receipt of the compact disc is required.

7.3 PATIENT-REPORTED OUTCOME DATA

Data from paper PRO questionnaires will be entered into the EDC system by site staff. Paper PRO questionnaires are source data and should be handled according to Section [7.4](#).

7.4 SOURCE DATA DOCUMENTATION

Study monitors will perform ongoing source data verification to confirm that critical protocol data (i.e., source data) entered into the eCRFs by authorized site personnel are accurate, complete, and verifiable from source documents.

Source documents (paper or electronic) are those in which patient data are recorded and documented for the first time. They include, but are not limited to, hospital records, clinical and office charts, laboratory notes, memoranda, patient-reported outcomes, evaluation checklists, pharmacy dispensing records, recorded data from automated instruments, copies of transcriptions that are certified after verification as being accurate and complete, microfiche, photographic negatives, microfilm or magnetic media, X-rays, patient files, and records kept at pharmacies, laboratories, and medico-technical departments involved in a clinical trial.

Before study initiation, data to be entered directly into the eCRFs (i.e., no prior written or electronic record of the data) and considered source data must be defined in the Trial Monitoring Plan.

Source documents that are required to verify the validity and completeness of data entered into the eCRFs must not be obliterated or destroyed and must be retained per the policy for retention of records described in Section 7.6.

To facilitate source data verification, the investigators and institutions must provide the Sponsor direct access to applicable source documents and reports for trial-related monitoring, Sponsor audits, and IRB/EC review. The investigational site must also allow inspection by applicable Health Authorities.

7.5 USE OF COMPUTERIZED SYSTEMS

When clinical observations are entered directly into an investigational site's computerized medical record system (i.e., in lieu of original hardcopy records), the electronic record can serve as the source document if the system has been validated in accordance with Health Authority requirements pertaining to computerized systems used in clinical research. An acceptable computerized data collection system allows preservation of the original entry of data. If original data are modified, the system should maintain a viewable audit trail that shows the original data as well as the reason for the change, name of the person making the change, and date of the change.

7.6 RETENTION OF RECORDS

Records and documents pertaining to the conduct of this study and the distribution of IMP, including eCRFs, ePRO data (if applicable), informed consent forms, laboratory test results, and medication inventory records, must be retained by the Principal Investigator for at least 15 years after completion or discontinuation of the study, or for the length of time required by relevant national or local Health Authorities, whichever is longer. After that period of time, the documents may be destroyed, subject to local regulations. No records may be disposed of without the written approval of the Sponsor. Written notification should be provided to the Sponsor prior to transferring any records to another party or moving them to another location.

8. ETHICAL CONSIDERATIONS

8.1 COMPLIANCE WITH LAWS AND REGULATIONS

This study will be conducted in full conformance with the ICH E6 guideline for Good Clinical Practice and the principles of the Declaration of Helsinki, or the laws and regulations of the country in which the research is conducted, whichever affords the greater protection to the individual. The study will comply with the requirements of the ICH E2A guideline (Clinical Safety Data Management: Definitions and Standards for Expedited Reporting). Studies conducted in the United States or under a U.S. Investigational New Drug (IND) application will comply with U.S. FDA regulations and

applicable local, state, and federal laws. Studies conducted in the EU/EEA will comply with the EU Clinical Trial Directive (2001/20/EC).

8.2 INFORMED CONSENT

The Sponsor's sample Informed Consent Form will be provided to each site. If applicable, it will be provided in a certified translation of the local language. The Sponsor or its designee must review and approve any proposed deviations from the Sponsor's sample Informed Consent Forms or any alternate consent forms proposed by the site (collectively, the "Consent Forms") before IRB/EC submission. The final IRB/EC-approved Consent Forms must be provided to the Sponsor for health authority submission purposes according to local requirements.

The Consent Forms must be signed and dated by the patient or the patient's legally authorized representative before his or her participation in the study. The case history or clinical records for each patient shall document the informed consent process and that written informed consent was obtained prior to participation in the study.

The Consent Forms should be revised whenever there are changes to study procedures or when new information becomes available that may affect the willingness of the patient to participate. The final revised IRB/EC-approved Consent Forms must be provided to the Sponsor for Health Authority submission purposes.

Patients must be re-consented to the most current version of the Consent Forms (or to a significant new information/findings addendum in accordance with applicable laws and IRB/EC policy) during their participation in the study. For any updated or revised Consent Forms, the case history or clinical records for each patient shall document the informed consent process and that written informed consent was obtained using the updated/revised Consent Forms for continued participation in the study.

A copy of each signed Consent Form must be provided to the patient or the patient's legally authorized representative. All signed and dated Consent Forms must remain in each patient's study file or in the site file and must be available for verification by study monitors at any time.

For sites in the United States, each Consent Form may also include patient authorization to allow use and disclosure of personal health information in compliance with the U.S. Health Insurance Portability and Accountability Act of 1996 (HIPAA). If the site utilizes a separate Authorization Form for patient authorization for use and disclosure of personal health information under the HIPAA regulations, the review, approval, and other processes outlined above apply except that IRB review and approval may not be required per study site policies.

